### 8.3. Hypothetical Diagnostic Pathways

The following hypothetical diagnostic pathways (HDPs) correspond to the other test performance (MRI and US) end point “comparison of different testing combinations in terms of biopsy rates, detection of insignificant cancer and significant cancers”. To assess the different testing combinations of PSA, ultrasound and MRI, the HDPs, displayed in Figure 1, map the suggested specifications and order of the screening tests to biopsy.

**Figure 1: Hypothetical diagnostic pathways (HDP) mapping suggested orders of screening tests (MRI, ultrasound and PSA) to biopsy**

Imperial Clinical Trials Unit	STATISTICAL ANALYSIS PLAN	PROSTAGRAM
-------------------------------	---------------------------	------------

## 9. Analysis Set

### 9.1. Evaluable Population for Analysis

Analysis will be carried out for the evaluable population. This is defined as those individuals who meet the eligibility criteria and complete at least one of the screening assessments (MRI, ultrasound or PSA).

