### 5.3.2. Exclusion Criteria

[figure not shown]
1. Previous PSA test or prostate MRI within the prior two years of screening/consent visit
2. Evidence of a urinary tract infection or history of acute prostatitis within the last 6 months
3. Previous history of prostate cancer, prostate biopsy or treatment for prostate cancer (interventions for benign prostatic hyperplasia/bladder outflow obstruction is acceptable)
4. Any potential contraindication to MRI, including but not limited to:
  - a. Devices or metallic foreign bodies such as pacemakers, implantable defibrillators, neurostimulators, cochlear implants, coronary stents, prosthetic heart valves, aneurysm clips and other intravascular devices
  - b. Previous history of hip replacement surgery, metallic hip replacement or extensive pelvic orthopaedic metal
  - c. Claustrophobia
5. Any potential contraindication to prostate biopsy
6. Dementia or altered mental status that would prohibit the understanding or rendering of informed consent.
7. Any other medical condition precluding procedures described in the protocol.

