		
 
• Bar charts displaying the proportions of participants who selected each Likert score, compared between screening tests, for each EBQ & PBQ component
 
• Paired t-tests comparing mean difference between pre- (EBQ) and post- (PBQ) screening test component scores, for each screening test
 
• Proportion of preference for each test as measured by EBQ (expected preference) and PBQ (final preference)
 
• Multivariable logistic regression on dichotomised test preference, for each screening test, controlling for patient related factors
 
• Summary statistics for the time taken for each test to be completed
 
• Proportion who undergo repeat screening assessments (MRI, ultrasound & PSA)
 
• Summary statistics of incidental findings
 
	
Other			
	Rates of biopsy related adverse events (infectious complications, urinary retention, and haematuria requiring admission)	Table of biopsy related adverse events (Section 10.3.7)	Participants who were biopsied 
Subgroup Analysis			
	Proportion of men with a screen-positive MRI defined by a score of 3 or greater (PIRADS)	
 
• Logistic regression model for MRI result (defined using PIRADS cut-off [1], see Section 10.3.1) on age
 
• Ordinal logistic regression model for PIRADS score on age
 
• Boxplots displaying the distribution of age across PIRADS scores
 
	Participants with MRI results 
	Proportion of men with a screen-positive MRI defined by a score of 4 or greater (PIRADS)	Logistic regression model for MRI result (defined using PIRADS cut-off [2], see Section 10.3.1) on age	Participants with MRI results 
	Proportion of men with a screen-positive prostate ultrasound defined by a score of 3 or greater (US)	
 
• Logistic regression model for ultrasound result (defined by US cut-off [1], see Section 10.3.2) on age
 
• Ordinal logistic regression model for US score on age
 
• Boxplots displaying the distribution of age across US scores
 
	Participants with ultrasound results 
	Proportion of men with a screen-positive prostate ultrasound defined by a score of 4 or greater (US)	Logistic regression model for ultrasound result (defined by US cut-off [2], see Section 10.3.2) on age	Participants with ultrasound results 

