Interobserver Agreement for MRI			

Imperial Clinical Trials Unit	STATISTICAL ANALYSIS PLAN	PROSTAGRAM
----------------------------------	---------------------------	------------

	Interobserver agreement for double reported MRI scans	
 
• Agreement of PIRADS scores for MRI scans between local and central readers 
 
• Cohen's Kappa statistic
 
 
 
	Participants whose MRI results were double reported  Double reported MRI scans
--	---	---	---

This population will satisfy the definition in Section 9.1

The use of parametric methods of analysis require stronger distributional assumptions. These can be evaluated for robustness using non-parametric methods. Firstly, an appropriate transformation will be considered if the assumption of normality is not met. This may involve a log transformation which provides transparent interpretation of effects in relative terms. Then, non-parametric methods will be considered and implemented if after an appropriate transformation the assumption of normality is still not met.

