### 11.3. Safety Analysis

At the final visit, the adverse and serious adverse events should be reconciled on the eCRF. Reported adverse events (AEs) and serious adverse events (SAEs) will be listed and summarised separately. A separate table will summarise study-related adverse events (see Appendix 3). Expected adverse events are listed in Appendix 3.

All other safety variables will be summarised by time point in the form of frequency tables for categorical variables or descriptive statistics for continuous variables.

Imperial Clinical Trials Unit	STATISTICAL ANALYSIS PLAN	PROSTAGRAM
-------------------------------	---------------------------	------------

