**Table 1.5. 2: Incidence of expected adverse events (see Appendix 3)**

Event class	Total - n (%)
Expected study-related adverse events:	xx (xx%)
Haematomas and ecchymoses around venepuncture site	xx (xx%)
Minor discomfort	xx (xx%)
Infection	xx (xx%)
Expected adverse events associated with MRI:	xx (xx%)
Claustrophobia	xx (xx%)
Anxiety/Stress	xx (xx%)
Discomfort	xx (xx%)
Expected adverse events associated with Prostate M-P US:	xx (xx%)
Minimal rectal discomfort during the procedure	xx (xx%)
Expected adverse events associated with Prostate Biopsy:	xx (xx%)
	xx (xx%)

Imperial Clinical Trials Unit	STATISTICAL ANALYSIS PLAN	PROSTAGRAM
-------------------------------	---------------------------	------------

Blood in urine (Haematuria)	xx (xx%)
Pain passing urine (Dysuria)	xx (xx%)
Blood in semen (Haematospermia)	xx (xx%)
Temporary pain/discomfort in the perineal area	xx (xx%)
Temporary problems with erections for up to 6-8 weeks	xx (xx%)
Retention of urine requiring a temporary catheter	xx (xx%)
Prostatitis	xx (xx%)
Infection requiring admission and intravenous antibiotics	xx (xx%)
Expected risks from undergoing local anaesthetic:	xx (xx%)
Nausea and vomiting	xx (xx%)
Minor bruises for intravenous catheters	xx (xx%)
Extensive bruising, temporary hardening of vein (phlebitis) or infection	xx (xx%)
Dizziness/Vertigo	xx (xx%)
Confusion/Disorientation	xx (xx%)
Respiratory depression and apnoea	xx (xx%)
Anaphylaxis to local anaesthetic	xx (xx%)
Expected risks from undergoing general anaesthetic:	xx (xx%)
Nausea and vomiting	xx (xx%)
Dry cough	xx (xx%)
Minor bruises from intravenous catheter	xx (xx%)
Extensive bruising, temporary hardening of the vein (phlebitis) or infection	xx (xx%)
Death	xx (xx%)
Other adverse event (specify):	xx (xx%)
...	xx (xx%)
Total	xx (xx%)

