**Table 2. 2: Number of protocol deviations and violations**

Type of Deviation/Violation	Total
Inclusion/exclusion criteria	xx (xx%)
Study drug administration	xx (xx%)
Sampling/laboratory measurements	xx (xx%)
Consent issue	xx (xx%)
Study visit windows	xx (xx%)
NIMP administration	xx (xx%)
Study drug prescription	xx (xx%)
Dispensing	xx (xx%)
Accountability	xx (xx%)
Compliance	xx (xx%)
Missed study visit	xx (xx%)

Imperial Clinical Trials Unit	STATISTICAL ANALYSIS PLAN	PROSTAGRAM
-------------------------------	---------------------------	------------

Study measurements/assessments	xx (xx%)
Primary outcome measure	xx (xx%)
Secondary outcome measure	xx (xx%)
Safety outcome	xx (xx%)
Device	xx (xx%)
Equipment	xx (xx%)
Prohibited medication/substance(s)	xx (xx%)
AE/SAE reporting	xx (xx%)
Blinding/unblinding	xx (xx%)
Randomisation	xx (xx%)
Implementation of document prior to research approval	xx (xx%)
Licence/certification/calibration/servicing (labs and equipment)	xx (xx%)
Delegation log/authorisation	xx (xx%)
Dose interruptions/modifications not specified in protocol	xx (xx%)
Variation in clinical management of participant	xx (xx%)
Withdrawal issue	xx (xx%)
Falsifying research or medical records	xx (xx%)
Repeated protocol deviations (of same type)	xx (xx%)
Other	xx (xx%)
Total deviations/violations	xx (xx%)
Total patients with at least one deviation/violation	xx (xx%)

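### The SAP's only analysis set requires eligibility and is applied to the biopsy adverse-event rate, and Table 1.5.2 gives no denominator for procedure-specific events

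*SAP*

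**What the plan says.** SAP 9.1 is the only place where an analysis set is defined. It reads "Analysis will be carried out for the evaluable population. This is defined as those individuals who meet the eligibility criteria", and adds completion of at least one of MRI, ultrasound or PSA. No safety set is defined anywhere.

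For rates of biopsy-related adverse events (infectious complications, urinary retention, haematuria requiring admission), SAP Table 1 gives the population as "Participants who were biopsied". That entry carries footnote 1: "This population will satisfy the definition in Section 9.1".

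The safety sections, SAP 11.3 and 14, say "Reported adverse events (AEs) and serious adverse events (SAEs) will be listed and summarised separately". They name neither a population nor a denominator, and they do not refer to 9.1.

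Table 1.5.2 is the shell for expected events. Venepuncture, MRI, ultrasound, "Expected adverse events associated with Prostate Biopsy", local anaesthetic and general anaesthetic each form a block. All blocks share one total column of counts and percentages, and no denominator is stated.

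Tables 1.5.1 and 1.5.6 are titled as listings of all adverse events and all serious adverse events.

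**The concern.** Harm is normally counted in everyone exposed to a procedure, whether or not they should have been enrolled. Here the eligibility condition is carried into the biopsy harm rate by an explicit footnote. A complication in a biopsied man later judged ineligible would leave the numerator, and the man would leave the denominator.

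The removal need not be neutral. The exclusions in SAP 5.3.2 include "Evidence of a urinary tract infection or history of acute prostatitis within the last 6 months" and any potential contraindication to biopsy, while the end point counts infection, retention and haematuria. It is plausible that these are related, in which case removal would tend to lower the reported rate. The documents do not quantify this.

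Table 1.5.2 raises a second, separate question. Every participant is scheduled for PSA, MRI and ultrasound, but only screen-positive men go to biopsy. A biopsy event divided by all evaluable men is not a biopsy complication rate, and the shell does not say which divisor is meant.

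Biopsy adverse events are a named end point of the primary paper (SAP 11.1.5), and limiting the harms of screening is part of the study's rationale (Protocol 1.1, SAP 2).

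**Working it through.** **Part 1: who is in the biopsy adverse-event rate.** This follows from reading three places together.
- Table 1: biopsied participants.
- Footnote 1 on that entry: they must also satisfy 9.1.
- 9.1: they must meet the eligibility criteria.

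The population is therefore men who are both biopsied and eligible.

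To show how sensitive the rate is to one event, take three events as an illustration, one of them in an ineligible man. That split is an assumption. The numbers biopsied are derived in Part 2.
- 82 biopsied: 3/82 = 3.7% becomes 2/81 = 2.5%.
- 234 biopsied: 3/234 = 1.3% becomes 2/233 = 0.9%.

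**Part 2: Table 1.5.2 if all evaluable men were the denominator.**

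The plan's sample size reproduces from n = z²P(1−P)/d², with z = 1.96 and d = 0.05:
- P = 0.196 gives 242.1, rounded up to 243.
- P = 0.611 gives 365.2, rounded up to 366.
- With 10% dropout, 243/0.9 = 270 and 366/0.9 = 406.7 (stated as 406).

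So 366 is the planned evaluable number.

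Inputs:
- Raised PSA 10.4%, normal PSA 89.6% (Protocol 9.1).
- MRI positive in 73% of raised-PSA men (Protocol 9.1).
- MRI positive in 13.37% or 59.75% of normal-PSA men, the protocol's two scenarios. SAP 6 adopts the higher one.
- Biopsy if any test is positive (SAP 8.2).
- Infection requiring admission 0.5–4% and retention 1 in 100 after biopsy (Protocol 7.10, SAP 20.3.4).

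Share of men positive on MRI or PSA = MRI-positive share + raised-PSA men with negative MRI:
- MRI-positive, low: 0.896 × 0.1337 + 0.104 × 0.73 = 0.1198 + 0.0759 = 0.1957.
- MRI-positive, high: 0.896 × 0.5975 + 0.104 × 0.73 = 0.5354 + 0.0759 = 0.6113.
- Raised PSA, MRI negative: 0.104 × 0.27 = 0.0281.
- MRI or PSA positive: 22.4% (low) and 63.9% (high).
- Men biopsied out of 366: 82 (low) and 234 (high).

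Percentage printed if the same events are divided by 366:
- 4% infection, low: 82 × 0.04 = 3.28 expected events; 3.28/366 = 0.9%.
- 4% infection, high: 234 × 0.04 = 9.36 expected events; 9.36/366 = 2.6%.
- 1% retention: 0.82/366 = 0.22% and 2.34/366 = 0.64%.
- Dilution factor: 1/0.2238 = 4.5-fold (low) and 1/0.6394 = 1.6-fold (high).

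Men positive only on ultrasound are left out because the documents give no ultrasound positivity rate. Including them would raise the number biopsied and reduce the dilution. Refusals of biopsy would do the opposite.

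**Part 3: the Table 1 biopsy end point.** Its population is biopsied men, so the factor in Part 2 does not apply to it.

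**The case against.** The strongest case on the other side is that this is a narrow drafting gap in a descriptive secondary analysis. Much of that stands.

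- A reader might infer that complications in ineligible men disappear from the report. The documents do not support that. Tables 1.5.1 and 1.5.6 are titled as listings of all events, SAP 10.4 records events without an eligibility limit, and Protocol 7.15 puts all recorded serious events in the annual report. Sections 11.3 and 14 do not cite 9.1, so whether 9.1 limits the listings is open. What is lost under the stated rule is the man's contribution to one rate. A listing does not replace a rate.
- A reader might infer that biopsy harm rates in general are diluted, or that the SAP makes all evaluable men the denominator of Table 1.5.2. It does neither. The pre-specified end point uses biopsied men. In Table 1.5.2 dilution is a risk because the denominator is unstated; 9.1 defines who is in the set, not the divisor of each row.
- Ineligible biopsied men may be very few, since criteria are verified at the clinic appointment before enrolment (SAP 5.3). This stands. Urinalysis for infection is a study laboratory evaluation (Protocol 5.6.1) and consent precedes further procedures, so an exclusion could still surface after enrolment.
- Table 2.2 has a row for "Inclusion/exclusion criteria", but it is weak evidence that such breaches are expected. The same table has rows for study drug administration and dispensing in a study that tests no drug, so it looks like a generic template.
- A reader might infer that Tables 1.4.1 and 1.5.2 would print the same event with two percentages. Mostly they count different things: any infectious complication against infection needing admission and intravenous antibiotics, and haematuria requiring admission against any haematuria. Only retention is close.

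**Conclusion.** The point holds in two limited parts.

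First, as written, the biopsy adverse-event rate excludes any biopsied man later found ineligible, together with his complication. This is a stated rule, not an omission. Its size cannot be computed because the documents give no expected number of such men. With few events expected, a single removal is visible in the rate, as the illustration shows. That the removed men carry higher risk is plausible but not stated in the documents.

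Second, Table 1.5.2 has no stated denominator. If all 366 men were used, a 4% biopsy infection rate would print as about 0.9% to 2.6%. The range rests on the protocol's two MRI scenarios, its 10.4% raised PSA and 73% MRI positivity within that group, full biopsy uptake, and no ultrasound-only positives. Under the adopted 61.1% prevalence the dilution is at the mild end, 1.6-fold, and most men are biopsied.

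The primary end point is untouched and safety is reported descriptively. This should be fixed, but it does not threaten the study. It is a free improvement.

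**What to change.** - Add to SAP 9.1 a safety population: all consented men who underwent at least one study procedure, regardless of eligibility.
- Name it as the population for sections 11.3 and 14 and for Tables 1.4.1 and 1.5.1 to 1.5.8.
- In Table 1, exempt the biopsy adverse-event row from footnote 1, so that its population is all biopsied men. State that denominator in Table 1.4.1.
- In Table 1.5.2, give each block its own denominator: men who had venepuncture, MRI, ultrasound or biopsy and, where it is recorded, men who had each type of anaesthetic.

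The cost is SAP wording and table-shell headers. The one possible limit is anaesthetic type: the Appendix 2 variable list does not show it, so the case report form should be checked. If it is not recorded for each man, biopsied men can serve as the labelled denominator for those two blocks. The change should be made before database lock, so that whose complications count is not decided after the data are seen.

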## 10. Variables of Analysis

### 10.1. Baseline Demographic Variables

After obtaining informed consent and registering the patient in the study, the following clinical and baseline assessments will be undertaken:

- Demographics such as: age, Index of Multiple Deprivation (IMD) quintile, BMI, ethnicity, qualification level, marital status, employment status, frequency of GP visits, smoking status and history, how the patient heard about the prostate check and, Digital rectal examination (DRE) results.
- Specific family, medical and prostate history.
- CCI and IPSS questionnaires (see Appendix 1).

#### 10.1.1. Recruitment Categories

The recruitment strategies listed in Section 2.5 will be grouped into 6 categories, as listed below, and then summarised:

- Letter from GP.
- GP Recruitment:
  - SMS/Text from GP
  - Verbal from GP.
- Traditional Recruitment:
  - Newspaper advert
  - Radio
  - Other.
- Social Media Recruitment:
  - [name] Twitter
  - Search engine/other internet source.
- Targeted Traditional Recruitment:
  - PROSTAGRAM team word of mouth/other word of mouth
  - Poster campaign.
- Targeted Social Media Recruitment:
  - [name] Facebook
  - Group messaging (WhatsApp).

### 10.2. Combined Questionnaire Scores

Overall (combined) and component (question) scores for each patient at each visit, for the following questionnaires, are required as part of the feasibility end point analysis:

- EBQ (for each screening test) (Visit 1)
- PBQ (for each screening test) (Visit 1).

Imperial Clinical Trials Unit	STATISTICAL ANALYSIS PLAN	PROSTAGRAM
-------------------------------	---------------------------	------------

Details of the questionnaires are included in Appendix 1.

### 10.3. Primary and Secondary End Point Variables

For more detailed information on the variables used in the analysis, please refer to Appendix 2.

#### 10.3.1. MRI Screening

MRI scores are recorded using two independent discrete scoring systems: Likert and PIRADS. Both of these are recorded on discrete scales from 1 to 5, and will be used in the analysis of MRI screening results. For each scoring system, two cut-offs defining a screen-positive MRI result will be evaluated.

##### Likert:

1. The presence of a discrete Likert score 3, 4 or 5 as scored by a radiologist.
2. The presence of a discrete Likert score 4 or 5 as scored by a radiologist.

##### PIRADS:

1. The presence of a discrete PIRADS score 3, 4 or 5 as scored by a radiologist.
2. The presence of a discrete PIRADS score 4 or 5 as scored by a radiologist.

Analysis of the primary end point will be repeated using each screen-positive cut-off definition, for both MRI scoring systems. Analyses of all other end points will be repeated for the two cut-offs defined by the PIRADS scoring system only. A biopsy will be carried out if at least one of the scores is screen-positive, even if there is disagreement between the scores.

The radiologist will report whether the MRI result was screen-positive or negative based on the PIRADS and Likert scores for each lesion.

If the question “Are there any lesions with an MRI score  $\geq 3$ ?” is recorded as “No”, on the MRI Reporting Form eCRF, then the MRI score (for both the Likert and PIRADS scoring systems) is classified as 1 or 2. This result would be categorised as a screen-negative result when using the first cut-offs for the two scoring systems above.

#### 10.3.2. Ultrasound Screening

Discrete ultrasound scores are recorded using the Ultrasound Score (US) scoring system and range from 1 to 5. Two cut-offs defining a screen-positive ultrasound result will be evaluated.

1. The presence of a discrete score of 3, 4 or 5 or prostate lesions on ultrasound.
2. The presence of a discrete score of 4 or 5 or prostate lesions on ultrasound.

Analysis will be repeated for each screen-positive cut-off.

The operator will report whether the ultrasound result was screen-positive or negative based on the US score for each lesion.

If the question “Are there any lesions scoring US score  $\geq 3$ ?” is recorded as “No” on the Ultrasound Reporting Form eCRF, then the US score is classified as 1 or 2. This result would be categorised as screen-negative when using the first cut-off above.

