### 4.2. Secondary End Points

#### 4.2.1. Other Test Performance End Points (MRI and US)

1. The proportions of men with a screen-positive MRI defined by a score of 4 or greater (Likert and PIRADS)
2. The proportion of men with screen-positive prostate ultrasound defined by a score of 3 or greater (US)
3. The proportion of men with screen-positive prostate ultrasound defined by a score of 4 or greater (US)
4. The proportion of men with raised PSA result defined by a recorded level of 3 ng/mL or greater
5. The proportion of participants within each MRI score or US score of 1, 2, 3, 4 or 5
6. An evaluation of proportion of participants across each MRI and US score with no cancer, insignificant cancer and significant cancer with each test
7. The proportion of participants across each PSA level (raised or normal) with no cancer, insignificant cancer and significant cancer
8. A comparison of the proportion of participants with a positive result for each screening test. A comparison of the proportion of men subsequently diagnosed with a clinically significant prostate cancer as defined by pre-specified histological definitions
9. Comparison of different testing combinations in terms of biopsy rates, detection of insignificant cancer and significant cancers
10. The correlation between imaging findings and DRE
11. The proportion of men who go onto definitive local or systemic treatment.

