**Table 1: Primary Outcome Paper End Point Analysis**

	End Point	Analysis	Population
Primary End Point			
	Proportions of men with a screen-positive MRI defined by a score of 3 or greater (PIRADS and Likert)	Proportion with positive MRI score defined by a cut-off $\geq 3$ (PIRADS cut-off [1] and Likert cut-off [1] in Section 10.3.1)	Participants with MRI results 
Other Test Performance (MRI and US)			
	Proportions of men with a screen-positive MRI defined by a score of 4 or greater (PIRADS and Likert)	Proportion with positive MRI score defined by a cut-off $\geq 4$ (PIRADS cut-off [2] and Likert cut-off [2] in Section 10.3.1)	Participants with MRI results 
	Proportion of men with a screen-positive prostate ultrasound defined by a score of 3 or greater (US)	Proportion with positive ultrasound score defined by a cut-off $\geq 3$ (US cut-off [1] in Section 10.3.2)	Participants with ultrasound results 
	Proportion of men with a screen-positive prostate ultrasound defined by a score of 4 or greater (US)	Proportion with positive ultrasound score defined by a cut-off $\geq 4$ (US cut-off [2] in Section 10.3.2)	Participants with ultrasound results 
	Proportion of men with raised PSA level (defined as PSA $\geq 3.0\text{ng/mL}$ )	Proportion with raised PSA level (Section 10.3.3)	Participants with PSA results 
	Proportion of participants within each MRI score or US score of 1, 2, 3, 4 or 5	
 
Proportion within each value of Likert score
 
Proportion within each value of PIRADS score
 
Proportion within each value of US score
 
Histograms of distribution of each score (Likert, PIRADS and US) (Sections 10.3.1 & 10.3.2)
 
	Participants who completed the relevant test for the respective analyses 
	Proportion of participants across each MRI and US score with no cancer, insignificant cancer and significant cancer for each test	
 
Proportion within each value of Likert score detected to have each type of clinical cancer (Sections 8.1 & 10.3.1)
 
Proportion within each value of PIRADS detected to have each type of clinical cancer (Sections 8.1 & 10.3.1)
 
	Participants biopsied, and who completed the relevant test for the

Imperial Clinical Trials Unit	STATISTICAL ANALYSIS PLAN	PROSTAGRAM

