**Table 1.2. 7: Proportion of men within each value of the discrete PIRADS score (MRI scoring system) and corresponding type of clinical cancer detected**

See Table 1.2. 6, but for discrete values of the PIRADS scoring system.

See Section 8.1 for definitions.

**Table 1.2. 8: Proportion of men within each value of the discrete ultrasound score (US) and corresponding type of clinical cancer detected**

See Table 1.2. 6, but for discrete values of the US scoring system.

See Section 8.1 for definitions.

**Table 1.2. 9: Proportion of men within each PSA level (raised and normal) and corresponding type of clinical cancer detected**

Definition 	Type of clinical cancer	PSA Level	
		Raised ( $\geq 3.0$ ng/ml)	Normal ( $< 3.0$ ng/ml)
i	Clinically significant cancer	xxx (xx%) x.xx to x.xx	xxx (xx%) x.xx to x.xx
	Clinically insignificant cancer	xxx (xx%) x.xx to x.xx	xxx (xx%) x.xx to x.xx
	No cancer	xxx (xx%) x.xx to x.xx	xxx (xx%) x.xx to x.xx
ii	Clinically significant cancer	xxx (xx%) x.xx to x.xx	xxx (xx%) x.xx to x.xx
	Clinically insignificant cancer	xxx (xx%) x.xx to x.xx	xxx (xx%) x.xx to x.xx
	No cancer	xxx (xx%) x.xx to x.xx	xxx (xx%) x.xx to x.xx
iii	Clinically significant cancer	xxx (xx%) x.xx to x.xx	xxx (xx%) x.xx to x.xx
	Clinically insignificant cancer	xxx (xx%) x.xx to x.xx	xxx (xx%) x.xx to x.xx
	No cancer	xxx (xx%) x.xx to x.xx	xxx (xx%) x.xx to x.xx
iv	Clinically significant cancer	xxx (xx%) x.xx to x.xx	xxx (xx%) x.xx to x.xx

	Clinically insignificant cancer	xxx (xx%) x.xx to x.xx	xxx (xx%) x.xx to x.xx
	No cancer	xxx (xx%) x.xx to x.xx	xxx (xx%) x.xx to x.xx
v	Clinically significant cancer	xxx (xx%) x.xx to x.xx	xxx (xx%) x.xx to x.xx
	Clinically insignificant cancer	xxx (xx%) x.xx to x.xx	xxx (xx%) x.xx to x.xx
	No cancer	xxx (xx%) x.xx to x.xx	xxx (xx%) x.xx to x.xx

See Section 8.1 for definitions.

See Section 10.3.3 for definitions.

**Table 1.2. 10: Comparisons of proportions of results between pairs of screening tests (MRI & ultrasound, MRI & PSA and ultrasound & PSA) using McNemar chi square tests**

McNemar's test statistic		MRI		Ultrasound		PSA
		Positive MRI (PIRADS ≥ 3) (Cut-off [1])	Positive MRI (PIRADS ≥ 4) (Cut-off [2])	Positive ultrasound (US ≥ 3) (Cut-off [1])	Positive ultrasound (US ≥ 4) (Cut-off [2])	Raised PSA (≥ 3.0 ng/ml)

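### SAP 10.3.2: a lesion clause with no score attached makes ultrasound cut-off [2] the same rule as cut-off [1], contradicting the score ≥4 meaning used elsewhere

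*SAP*

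**What the plan says.** SAP 10.3.2 gives two cut-offs for a positive ultrasound. The first is a score of 3, 4 or 5, or lesions seen on ultrasound. The second is "The presence of a discrete score of 4 or 5 or prostate lesions on ultrasound". Neither lesion clause has a score attached.

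The same section ties the score to the lesion: "The operator will report whether the ultrasound result was screen-positive or negative based on the US score for each lesion". It also says how to code a negative answer to the eCRF question about any lesion scoring 3 or more: "then the US score is classified as 1 or 2. This result would be categorised as screen-negative when using the first cut-off above".

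Elsewhere cut-off [2] is a score rule only:

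- SAP 4.2.1, 11.1.3 and 11.4.1 state the end point as a score of 4 or greater.
- SAP Table 1 describes the analysis as a cut-off of ≥4 and cites "US cut-off [2] in Section 10.3.2" as its source.
- The shells for Tables 1.2.2 and 1.2.10 to 1.2.12 label cut-off [2] as ≥4. Table 1.2.13 follows the layout of 1.2.12.

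The parallel MRI rule in 10.3.1 has no lesion clause: "The presence of a discrete PIRADS score 4 or 5 as scored by a radiologist".

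**The concern.** Two thresholds are meant to be compared, but the text that defines them makes them one threshold. An objective in SAP 3.2.1 is to evaluate a suitable score threshold for ultrasound, and another is to explore test combinations for a future study. Both need a cut-off [2] that differs from cut-off [1].

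If 10.3.2 is programmed as written, every analysis that cites cut-off [2] is affected: the ≥4 positive rate, the McNemar tests, sensitivity and specificity, the false-positive proportions, the treatment proportions and the age models. In Tables 1.2.2 and 1.2.10 to 1.2.13 the ≥3 and ≥4 results stand side by side, so identical values would give the error away. Table 1.2.15 has no ≥4 label but does show both cut-offs.

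The pathway analysis (SAP 11.2.3 and Table 1.2.14, footnote 4) has neither safeguard in the visible text. It uses cut-off [2] alone, by reference to 10.3.2. Figure 1 in SAP 8.3, which is meant to "map the suggested specifications and order of the screening tests to biopsy", is not visible in the text available and may state the threshold.

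**Working it through.** **Set logic.** Define:

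- L = men with any lesion on ultrasound
- S3 = men whose highest lesion score is 3 or more
- S4 = men whose highest lesion score is 4 or more

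Scores attach to lesions (SAP 10.3.2; Protocol 6.4 also speaks of lesions being scored). So S4 lies within S3, and S3 lies within L.

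- Cut-off [1] as written = S3 or L = L
- Cut-off [2] as written = S4 or L = L
- Cut-off [2] as labelled elsewhere = S4

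| Man | [1] as written | [2] as written | Score ≥4 |
|---|---|---|---|
| No lesion | negative | negative | negative |
| Only lesions scored 1–2, if such lesions are recorded | positive | positive | negative |
| Highest lesion score 3 | positive | positive | negative |
| Highest lesion score 4 or 5 | positive | positive | positive |

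Crossing the five scores with lesion present or absent gives ten combinations. The two written rules differ in only one of them, a score of 3 without a lesion, which per-lesion scoring should not produce.

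The second row also bears on cut-off [1]. If lesions scored 1–2 are recorded, such a man is positive by the clause but negative by the eCRF rule in the same section.

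**Excess at cut-off [2].** L minus S4 = men whose highest score is 3, plus any men with only lesions scored 1–2. The documents give no ultrasound score distribution, so the count cannot be derived. Scaling on the planned numbers in SAP section 6:

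- Per 1% of scanned men: 0.01 × 366 = 3.66; 0.01 × 406 = 4.06.
- Assumed 5%: 0.05 × 366 = 18.3.
- Assumed 20%: 0.20 × 366 = 73.2.

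The 5% and 20% are illustrations only. These figures apply to the proportion among all scanned men (Table 1.2.2). SAP Table 1 limits the pathway analysis to biopsied men, whose number is not given, so no pathway figure is offered.

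**Pathways exposed.** In Table 1.2.14 the pathways that include ultrasound are: ultrasound alone; PSA and ultrasound; ultrasound and MRI; PSA, ultrasound and MRI. That is 4 of 7.

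**The case against.** The strongest reply is that the intent is plain and a competent programmer would recover it. SAP 10.3 sends the reader to Appendix 2 for variable detail. There the ≥4 ultrasound end point lists only the ultrasound score, while the ≥3 end point also lists the binary overall result. No lesion-presence variable is named. Table 1 labels the cut-off ≥4, and 11.2.3 introduces the ultrasound rule as the counterpart of a pure PIRADS 4-or-5 rule. If one derived variable serves every table, an error visible in Table 1.2.2 would also be caught for the pathways.

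Much of this stands as evidence of intent. It does not correct 10.3.2, which Table 1, 11.2.3 and the pathway footnote all cite as the definition. Nor does Appendix 2 settle the pathways, since for them it lists both the score and the binary overall result. Two programmers could follow different parts of the SAP and both claim compliance.

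Two narrower objections have some force. First, the documents do not show that lesions scored 1–2 are recorded. If they are not, the clause in cut-off [1] is redundant rather than contradictory. The collapse of cut-off [2] into cut-off [1] does not depend on this. Second, cut-off [1] repeats the ultrasound wording of SAP 8.2, so editing it leaves the two sections worded differently. That is a reason to coordinate the edits. It is not a reason to keep an unscored clause in an analysis definition whose end point is stated by score.

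**Conclusion.** The concern holds. Read as written, the two ultrasound cut-offs in SAP 10.3.2 classify men identically, and cut-off [2] contradicts the score ≥4 rule used in the end points, Table 1 and the labelled shells. The one premise is that a score of 3 implies a lesion, which 10.3.2 and Protocol 6.4 support.

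The numerical effect is unknown. It equals the men whose highest score is 3, plus any with only lesions scored 1–2. The importance does not rest on the assumed range: a stated decision threshold is wrong in the section that defines it.

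The reach is limited. The primary MRI end point, the sample size and the per-score ultrasound tables (1.2.5 and 1.2.8) are not affected, and the pathway outputs are descriptive. This is a correction to make before programming and does not threaten the main result.

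**What to change.** - In SAP 10.3.2, delete the lesion clause from both lines. Cut-off [1] becomes a maximum US score of 3, 4 or 5, and cut-off [2] a maximum US score of 4 or 5. This agrees with 4.2.1, Table 1, the labelled shells and the eCRF rule.
- In SAP 11.2.3 and in footnote 4 of Table 1.2.14, write US score ≥4 beside the reference to cut-off [2]. Check that Figure 1 in 8.3 agrees.
- Separately, the ultrasound trigger for biopsy is worded differently in Protocol 6.4, Protocol 6.6 and SAP 8.2. The sponsor should reconcile these passages; no view is taken here on which rule is right.

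The cost is two edited lines and two short insertions before programming, with no new data and no change to the sample size. Reconciling the biopsy wording is a further task for the sponsor.
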